Patients will be seen by the treating physician on the day of SRS, and on subsequent follow-up visits. They will be followed closely with clinical and imaging exams for safety and tumor recurrence (i.e., 1 month, 3 months, 6 months post-SRS). All treatment-related toxic effects and adverse events will be recorded according to NCI Common Terminology Criteria for Adverse Events, version 4.0. Local tumor control rates for each treated lesion will be assessed according to the revised Response Assessment in Neuro-oncology (RANO) criteria^{81,82}.

Payment

Parking for study patients related to study visits will be complementary. Subjects will be compensated \$100 for participation in this study to help compensate for time and travel costs.

Statistical Considerations

Primary Objective Analysis:

Cognitive test results (pre- and post-SRS) will be scored based on standardized published norms^{72,87}. Cognitive deterioration will be defined as a decline of greater than 1 SD on at least 1 of the 7 cognitive tests (Table 2, not including BDI or FACT-BR). Fisher's exact 2-group binomial test will be used to compare the proportion of patients with 3-month post-SRS cognitive deterioration between the current cognitive-sparing SRS study and previously reported with standard SRS.⁵ Further analyses of pre- to post-SRS cognitive change for each test will

utilize a reliable change index (RCI)⁸⁷. This index is derived from the standard error of measurement of each test, and it represents the 90% confidence interval (CI) for the difference in raw scores from baseline to follow-up that is expected if no real change has occurred. RCI values below the 90% CI are indicative of significant decline. RCIs also account for practice effects, which is ideal for this study where evaluations are 3 months apart. One-sample t-tests ($H_0=0$) will be used to determine significant group decline in RCIs by test and cognitive domain. Pearson correlation coefficients will be used to assess associations between RCIs and depression scores. Bonferroni corrections will be applied to control for Type I errors due to multiple comparisons.

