With RCI at 3-months post-SRS as the outcome variable, linear regression modeling will be used to analyze patient-specific (e.g. age, sex), tumor-specific (e.g. histology, number of lesions, imaging progression), and treatment-specific (e.g. previous chemotherapy, anti-epileptic drugs) predictors of neurocognitive change after cognitive-sparing SRS. Model selection will be based on Akaike Information Criterion (AIC)^{88,89}. Given the small sample size and multiple variables of interest, this will be an exploratory analysis. Given that cognitive-sparing on this study will not be performed at the sacrifice of tumor coverage, we expect the overall local control and survival rates in the cohort to be comparable to those in other studies of SRS alone for patients with 1-3 brain metastases^{1,5,6,22}. Treated tumor local control rates will be assessed at 3- and 6-months post-SRS. Local tumor control of each treated lesion will be assessed with modified RANO criteria⁸⁴ where tumor progression is defined as >25% increase in the size of a treated lesion. Tumor progression of treated metastases will be evaluated independently of the development of new lesions⁵. Local tumor control rate at 6 months and overall survival rate (death from any cause) at 12 months will be compared to historical values⁵ using a 1-sample t-test.

Secondary Objective Analyses

The imaging biomarker of each structure (mean white matter diffusivity metrics and hippocampal volume) will be modeled as a function of time using linear mixed effect models^{13,16}. These models are well-suited for longitudinal analysis since they account for within-subject correlation between repeated measures, and allow for incomplete outcome data. Individual structures will be classified based on whether they received greater or less than the median dose for that structure across all patients. The interaction of dose and time will be tested within the model to assess whether dose mediates longitudinal trends. In addition, potential fixed-effect covariates will be selected from a list of patient and tumor-specific variables, such as age, sex, tumor size and location. Model selection will be based on AIC. To account for correlated observations within subjects, patient-specific random intercepts and time-associated slopes will be tested.

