Sample Size Determination: This study is powered based on the endpoint of cognitive deterioration at 3 months post-SRS, defined as decline of greater than 1 standard deviation (SD) from baseline on at least 1 of the neurocognitive tests. This was the primary endpoint of the Alliance N0574 study. With 60 accrued patients

and assuming a 20% drop-out rate, we will have sample size $n=48$. We have 85% power to detect a change in the cognitive deterioration rate from 64% in standard SRS to 42.5% in the current cognitive-sparing study with $n=48$ (Fisher's exact 2-group binomial test, 2-tailed $\alpha=0.05$).

4. Risks

The anticipated risk to patients in this study is minimal.

The MRI scans to be obtained at baseline would be added on to the same scan performed for routine SRS planning for patients. Follow up MRI would be standard of care imaging and would be obtained regardless of whether the patient is on or off study. These scans do not involve any radiation exposure. There are no additional risks associated with the research scans aside from discomfort due to the additional 8-10 minutes of scan time required. However, these scans are frequently performed as part of standard of care during presurgical planning without adverse effects. Some patients may experience claustrophobia in the MR scanner and may require the use of medications for this, as is prescribed routinely for brain MRIs when indicated.

Intracranial SRS would be performed identically to standard of care, except for adding additional regional avoidance for cognitive sparing. In cases where sparing of these structures cannot be performed without sacrificing treatment of the tumor or another critical structure, this will be recorded and the default will be the standard clinical plan. While clinical benchmarks of SRS quality will not be sacrificed on this study, there is a possibility that changing the SRS plan to achieve cognitive sparing may change the dose distribution to other structures in the brain. It is unclear whether this would change any clinical outcomes since SRS plans must adhere to the same rigorous standards as the current standard of care.

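### Local control and survival are compared with historical rates treated as error-free, so the test rejects above its nominal level by an amount set by a historical sample size the protocol does not give

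*Protocol*

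**What the plan says.** The Primary Objective Analysis, under Statistical Considerations, introduces the two outcomes with an expectation: because tumour coverage is not to be given up, "we expect the overall local control and survival rates in the cohort to be comparable to those in other studies of SRS alone" in patients with 1 to 3 brain metastases. It then names the two quantities, "Local tumor control rate at 6 months and overall survival rate" at 12 months, and the method: "overall survival rate (death from any cause) at 12 months will be compared to historical values⁵ using a 1-sample t-test". Reference 5 is the randomized trial of SRS with or without WBRT that also supplies the historical control for cognition. Local control is assessed lesion by lesion, and a patient may have one to three lesions.

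Earlier in the same section, the primary endpoint is compared with the same trial in another way: "Fisher's exact 2-group binomial test will be used to compare the proportion of patients with 3-month post-SRS cognitive deterioration" between this study and the published standard-SRS result.

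The protocol gives no historical local control or survival rate, no number of historical patients or lesions, no margin for comparability, and no significance level for these two tests. The only level stated, in Sample Size Determination, belongs to the primary endpoint: "Fisher's exact 2-group binomial test, 2-tailed $\alpha=0.05".

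**The concern.** The question behind these comparisons is whether control and survival after cognitive-sparing SRS match those after standard SRS. A 1-sample test answers a narrower one: does the study rate equal the number the historical trial happened to report? That number has its own sampling error, and a 1-sample standard error leaves it out. The resulting interval is too narrow for the intended question, and a historical estimate that was high or low by chance can appear as a loss or a gain in this study.

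This is distinct from whether a t-test suits binary, clustered or censored data. An exact binomial test or a 1-sample Kaplan-Meier test against the same fixed number would omit the historical error too.

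What is at stake is moderate. Neither outcome is the powered endpoint, but these are the only formal comparisons offered on whether sparing costs tumour control or survival. The protocol itself says that sparing may alter dose to other structures, with unclear clinical effect.

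**Working it through.** **Is there a figure of the plan's own to reproduce?** Not for these outcomes: no power or error rate is given for local control or survival. The only power figure (85%) concerns cognition and is taken up in the objection.

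**Inputs**
- Study size: "With 60 accrued patients" and, "assuming a 20% drop-out rate, we will have sample size $n=48" (60 × 0.8 = 48). The 48 is the evaluable number for the cognitive endpoint. I use 48 and 60 as a range.
- Level: two-sided 5%, assumed to carry over from the primary endpoint.
- Historical group size m: not in the protocol, so varied from 50 to 1000.
- True rates, for the exact check only: 50% for survival and 85% for local control. Both are assumptions.

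**Step 1. Normal approximation.** Let both groups have the same true rate p. The variance of (study rate − historical rate) is p(1−p)(1/n + 1/m), but the 1-sample test uses p(1−p)/n. The true standard error is therefore √(1 + n/m) times the one used, and

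rejection rate = 2 × [1 − Φ(1.96 / √(1 + n/m))].

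Example, n = 60 and m = 100: √1.6 = 1.265; 1.96/1.265 = 1.549; rate 12.1%.

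| m | n = 48 | n = 60 |
|---|---|---|
| 50 | 16.2% | 18.6% |
| 75 | 12.6% | 14.4% |
| 100 | 10.7% | 12.1% |
| 150 | 8.8% | 9.8% |
| 200 | 7.8% | 8.6% |
| 300 | 6.9% | 7.4% |
| 1000 | 5.6% | 5.7% |

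**Step 2. Where the rate is two to three times nominal.** Setting the rate to a and solving gives m = n / ((1.96/z)² − 1), where z is the two-sided normal quantile for a. For a = 10% (z = 1.645), m is about 114 (n = 48) or 143 (n = 60). For a = 15% (z = 1.440), m is about 56 or 70. The two-to-three-fold range thus needs m of 56-114 or 70-143. Over m = 50 to 1000 the multiple runs from about 1.1 to 3.7.

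**Step 3. Exact check with the t-test.** I enumerated the study count X ~ Bin(n, p) and the historical count Y ~ Bin(m, p), and rejected when |X/n − Y/m| / √(p̂(1−p̂)/(n−1)) exceeds the t quantile, with p̂ = X/n.

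| Reference | Survival, n = 60, p = 50% | Local control, n = 48, p = 85% |
|---|---|---|
| truly known | 5.2% | 6.6% |
| m = 50 | 18.2% | 15.8% |
| m = 75 | 13.8% | 12.5% |
| m = 100 | 11.9% | 11.2% |
| m = 150 | 9.5% | 9.7% |
| m = 200 | 8.4% | 9.5% |

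**Step 4. Direction of the error for local control.** With a truly known reference, the 6.6% is 5.7% false gain and 0.9% false loss. That asymmetry comes from using a t-test on yes/no data at a high rate. At m = 100 the 11.2% is 8.5% false gain and 2.7% false loss. False loss is 5.1% at m = 50 and 1.8% at m = 200, against 2.5% nominal per tail. The calculation treats patients as independent and does not model lesions within patients.

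**Step 5. Treating the historical arm as a sample.** In the same two settings, a pooled 2-group z-test rejects 4.8% to 5.2% of the time over m = 50 to 500.

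**The case against.** The strongest reply is that testing a single arm against a fixed benchmark is a conventional design with its nominal error for that null, and that the protocol does speak of historical values. This would settle the matter if a benchmark had been set. None is: the protocol gives no target value and frames the outcomes as comparability with other SRS-alone studies. What stands is that the sponsor may choose a fixed benchmark, provided it is named and the conclusion is confined to it.

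The second reply concerns size, and it stands. A reader might infer that the test always rejects at two to three times 5%. The documents do not support that, because m is not given and the level is itself carried over. Nor can the local control excess be put down wholly to historical error: 6.6% arises with a known reference, and for m of 100 or more the chance of falsely declaring a loss is close to or below 2.5% at the inputs used. Historical error does still raise that tail from 0.9%.

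Third, the primary endpoint is a weaker precedent than it looks. The plan says "We have 85% power to detect a change in the cognitive deterioration rate from 64% in standard SRS to 42.5"%, and attributes this to a 2-group Fisher test. With 48 against 48 that test gives about 49%. The stated figure appears when 64% is held constant: 0.215 / √(0.425 × 0.575 / 48) = 3.01, and Φ(3.01 − 1.96) = 85.4%. So the protocol's handling of this source is unsettled even there. The inconsistency of the named tests remains, but the argument here rests on the missing variance and not on the precedent.

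Fourth, a 2-group comparison has less nominal power to see harm. If survival were 35% against 50% (n = 60, m = 100), power to detect the loss falls from 63% to 46%. Part of the 63% is inflated size, but the cost is real and should be stated.

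**Conclusion.** The concern holds in this form. As a test of equal true rates, the 1-sample comparison omits the historical sampling error and rejects above its nominal level for any finite historical group to which the normal approximation applies. Under a two-sided 5% level and 48 to 60 independent patients, the rate is about 16-19% at m = 50, 11-12% at m = 100, 8-9% at m = 200 and under 6% at m = 1000. A twofold-to-threefold excess is conditional on m of roughly 56-114 (n = 48) or 70-143 (n = 60).

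The survival figures assume complete 12-month follow-up of all 60 patients. The local control figures assume one independent outcome per patient, whereas the protocol assesses each lesion.

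The point should be corrected but does not threaten the primary analysis. Because the protocol expects comparability and sets no margin, reading a non-significant result as reassurance is at least as serious a risk as excess rejection, and a change of test alone would not cure it.

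**What to change.** In the Primary Objective Analysis, replace the 1-sample t-test by an estimated difference from the historical SRS-alone arm, with a 95% interval that includes the historical sampling error:

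- **6-month local control:** a two-sample interval for a difference in proportions (Miettinen-Nurminen or Newcombe) from the published counts, with both sources on the same unit, patient or lesion. If the unit is the lesion, allow for lesions within a patient.
- **12-month survival:** the difference in Kaplan-Meier estimates, with SE = √(SE_study² + SE_historical²), taking the historical SE from the published interval or numbers at risk.
- **Interpretation:** state that a non-significant difference will not be read as comparability, and judge comparability from the interval.

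If a fixed benchmark is intended instead, name its value and limit the conclusion to that benchmark.

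The cost is wording, with no new patients or study data, provided the historical publication reports the counts and interval needed; that cannot be checked from the protocol. At m = 100 the intervals become about 1.2 to 1.3 times wider (√1.48 = 1.22 for n = 48; √1.6 = 1.26 for n = 60), with the loss of nominal power shown above.

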Brain metastases affect one third of all adult cancer patients¹. Stereotactic radiosurgery (SRS), a highly precise modality for focal ablative radiotherapy, is standard of care for patients with limited brain metastases¹⁻². However, many patients will experience decline in neurocognitive function after brain SRS^{3,4,5,6}, given the potential for high doses to eloquent brain tissue. Neurocognition has emerged as a critical endpoint along with survival and tumor control in brain tumor clinical trials^{7,5,8}. Radiation-induced cognitive impairment after SRS can manifest as a range of cognitive problems, particularly deficiencies in memory, language, attention and executive functioning, depending on tumor location and dose delivered to critical brain tissue.

Any focal intervention in the brain should occur with a detailed understanding of the brain's functional and anatomic relationships relative to the target⁹⁻¹⁰. With the aid of modern magnetic resonance imaging (MRI) techniques, eloquent brain regions can be well demarcated in imaging studies and projected into three-dimensional (3D) space. In particular, diffusion tensor imaging (DTI) tractography with automated white matter segmentation can be used to identify critical white-matter pathways (tracts) of the brain^{11,12,13}. 3-D volumetric MRI and automated brain parcellation software can be used to segment discrete areas of the brain including the hippocampus, a structure critical for memory^{14,15}. In radiation planning, particularly in brain SRS planning, these new technologies have **not yet** been prospectively tested for sparing healthy and sensitive parts of the brain from high doses of radiation.

These novel imaging techniques also allow us to directly and non-invasively measure microstructural changes after radiotherapy to critical brain structures *in vivo*. Using diffusion imaging biomarkers, we have shown that radiation therapy results in dose dependent damage to uninvolved white matter¹⁶ with greater susceptibility to injury among white matter tracts critical for neurocognition¹⁷. Our studies with 3-D volumetric MRI and automated parcellation of the hippocampus have shown dose-dependent hippocampal atrophy after fractionated brain radiotherapy^{15,18}. These imaging biomarkers hold promise to help elucidate the mechanisms behind radiation-induced cognitive decline.

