In this study, we propose a novel approach to cognitive-sparing brain SRS. Specifically, we will incorporate eloquent white matter tracts and hippocampal volumes obtained from DTI and volumetric MRI, respectively, into brain SRS planning in a cohort of patients with brain metastases. We will use innovative, advanced image acquisition and robust, automated image processing techniques. Cognitive outcomes, specifically language, memory, attention, and executive functioning, along with imaging tests to measure microstructural changes in these eloquent areas will be prospectively assessed, along with tumor control.

The primary objectives of this study are: **1).** To evaluate whether the relative sparing of eloquent white matter tracts (those critical for memory, language, attention, and executive functioning) and hippocampal volumes from high doses during brain SRS results in improved 3-month post-SRS cognitive performance relative to historical controls among patients with 1 to 3 brain metastases and **2.)** To measure longitudinal trends in white matter damage (using diffusion imaging) and hippocampal atrophy (using volumetric change) among patients receiving cognitive-sparing brain SRS and correlate these imaging biomarkers with domain-specific cognitive outcomes.

2. Background and Significance

The incidence of brain metastases is rising, and they currently affect up to **one-third of all adult cancer patients**, most commonly among lung, melanoma, renal cell, and breast cancer primaries¹. As novel systemic therapies improve survival rates and systemic disease control in cancer patients, brain metastases become a greater burden: these therapeutic agents poorly cross the blood-brain-barrier, creating a sanctuary site in the brain to harbor metastatic disease. At the same time, targeted therapeutics have changed the prognoses associated with brain metastases patients from the historically dismal few months¹⁹ to several years for certain groups who receive targeted agents and radiotherapy²⁰. This has transformed the paradigm of management for brain metastases patients from rapid palliation to treatments with durable local control and few long-term side effects.

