Radiation Planning Dose Constraints: As of yet, there are no evidence-based dose constraints for cognitive-sparing in brain SRS. Rational dose tolerances in clinical trials (a dose which predicts a particular likelihood of dysfunction) must be calculated based on normal tissue complication probability (NTCP) analyses⁷⁸. Hippocampal dose constraints used in WBRT trials²⁵ are not relevant to SRS (where high ablative doses are delivered) given that the prescription dose is so low in WBRT (30Gy in 10 fractions). In another IRB-approved longitudinal, prospective, observational study of primary brain tumor patients receiving definitive fractionated radiotherapy, we have been prospectively tracking domain-specific cognitive decline with all the standard cognitive measures in Table 1. Based on preliminary NTCP analyses from 28 patients, we found that maximum dose to the left hippocampus >28Gy (in 30 fractions) predicted for a >10% risk of significant decline (reliable change index <90% confidence interval) in HVLTR total and HVLTR delayed memory scores (p=0.01). Conversion of this maximum dose to a single fraction SRS dose constraint based on the linear quadratic formalism with $\alpha/\beta=2.5$ Gy for normal brain tissue yields a hippocampal maximum dose of 8.4Gy. This conversion was performed by solving for isoeffective dose by equating biologically effective doses from SRS single-fraction treatment, D_{SRS} , and reference fractionation, dose D_{ref} , delivered in N_{ref} fractions (set to 30):

$$D_{ref} \left(1 + \frac{D_{ref}}{\alpha/\beta} \right) = D_{SRS} \left(1 + \frac{D_{SRS}}{\alpha/\beta} \right)$$

For white matter tracts, within the left parahippocampal cingulum, V45Gy at 20.6% was predictive of significant decline on HVLTR total and HVLTR delayed memory scores (p=0.001). Conversion of this to a single fraction SRS dose constraint with $\alpha/\beta=2.5$ Gy for normal brain tissue (same method as above) yields a white matter maximum dose of 12Gy. Furthermore, a recently published analysis of SRS dose tolerances for the optic pathway (another critical white matter tract) established 12Gy in 1 fraction maximum dose as resulting in <1% risk of radiation-induced optic nerve neuropathy, supporting this white matter constraint. Dose constraints for single fraction SRS are summarized in Table 3. For lesions receiving 3 fractions, isoeffective dose constraints from Table 3 will be calculated based on $\alpha/\beta=2.5$ Gy.

Table 3: Dose Constraints

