Eloquent Cognitive Structures	Max Dose (Gy)
Cingulum	12
Uncinate Fasciculus	12
Inferior longitudinal fasciculus	12
Corpus Callosum	12
Arcuate fasciculus	12
Inferior frontostriatal tracts	12
Fornix	12
Hippocampus	8.4

*all bilateral except Corpus Callosum

SRS planning, plan optimization, and treatment: Patients will undergo setup, immobilization and simulation for frameless linear accelerator-based intracranial SRS with non-coplanar volumetric modulated arc radiosurgery (VMAR) as previously described⁷⁹. White matter and hippocampal 3D segmentations will be imported into the Eclipse treatment planning software (Varian Medical Systems, Palo Alto, California) for each patient. High-resolution, distortion-corrected stereotactic-protocol contrast-enhanced T1-weighted images will be co-registered with CT. Target volumes (enhancing tumor + 1mm margin for planning target volume, PTV) and standard organs at risk (OARs), such as the brainstem, optic nerves, and optic chiasm, will be manually contoured by the treating radiation oncologist. Tolerance doses for SRS planning include the white matter and hippocampal doses above, and standard single fraction dose constraints for other OARs as previously published⁸⁰. Prescription doses to each target lesion will be based on volume: 24 Gy in a single fraction if the target is less than 1 cc, 22Gy for 1.1-4cc target, and 20Gy for those between 4.1-10cc. For larger lesions or tumor beds, fractionated SRS with 24Gy in 3 fractions will be used respecting the constraints above. These doses closely follow a large Japanese SRS study²² with modern target volume-based doses, and are also similar to the Alliance N0574 trial⁵.

Automated knowledge-based brain SRS plans will be generated as previously described⁶⁹, with dose optimized within standard clinical guidelines (98% of the PTV receiving 100% of the prescription dose^{34,36}) and tolerance OAR doses above. Dose volume histograms will be assessed and re-optimized if necessary, without compromising coverage of tumor or sparing of standard critical structures (i.e. brainstem, optic structures.). All plans will be reviewed by the PI and the UCSD CNS Radiosurgery team for approval. Treatment delivery will follow the UCSD standard frameless brain SRS protocol⁷⁹.

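### The dose-by-time test for imaging change splits dose at the sample median although dose in Gy is available; the test is valid but inefficient and gives no effect per Gy

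*Protocol*

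**What the plan says.** The second objective in the protocol's introduction is "To measure longitudinal trends in white matter damage (using diffusion imaging) and hippocampal atrophy (using volumetric change) among patients receiving cognitive-sparing brain SRS", together with relating those changes to cognition. The analysis is under Statistical Considerations, Secondary Objective Analyses. Each structure's biomarker "will be modeled as a function of time using linear mixed effect models", and "patient-specific random intercepts and time-associated slopes will be tested". On dose, the section says "Individual structures will be classified based on whether they received greater or less than the median dose for that structure across all patients". The next sentence is "The interaction of dose and time will be tested within the model to assess whether dose mediates longitudinal trends". The classification has no other stated use, so the dose term in that interaction is binary.

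The dose itself is known. Under SRS planning, plan optimization, and treatment, the tract and hippocampal segmentations go into the planning system for each patient, and "Dose volume histograms will be assessed and re-optimized if necessary". Table 3 gives the limits for these structures in Gy: 12 for each white matter tract and 8.4 for the hippocampus. Some lesions are treated in three fractions. For these, Radiation Planning Dose Constraints says "For lesions receiving 3 fractions, isoeffective dose constraints from Table 3 will be calculated based on" an alpha/beta of 2.5 Gy.

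**The concern.** A continuous exposure is reduced to two levels before it is tested. Every structure above its median is treated as having the same dose, and likewise every structure below it. The introduction cites the group's own earlier work: "we have shown that radiation therapy results in dose dependent damage to uninvolved white matter". That suggests a graded relation, and nothing in the protocol points to a step at the sample median.

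Two things are at stake. If the relation is graded, the planned test is less likely to find it, in a study of only 60 patients. And the result is a contrast between two halves of the sample. Its cut point differs by structure, depends on who was enrolled and need not lie near either planning limit. The protocol states that evidence-based constraints for cognitive sparing in SRS do not yet exist. An estimate of change per unit of dose would bear on that gap, and the split cannot supply one.

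**Working it through.** The protocol states no power, effect size or dose distribution for this interaction, so there is no figure to reproduce. The dose shapes, the 80% reference power and the use of two-sided alpha 0.05 for this test are assumptions.

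**Information kept by the split.** If the biomarker slope is linear in dose X, the efficiency of the split relative to continuous dose is E = corr(X, 1[X > median])². For a normal dose this is 2/π = 0.637. If the continuous test has 80% power, power after the split is Φ((1.960 + 0.842)·√E − 1.960).

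| Assumed dose shape | E | Information lost | Power after split |
|---|---|---|---|
| Two-peaked, beta(0.5, 0.5) | 0.81 | 19% | 71% |
| Uniform | 0.75 | 25% | 68% |
| Normal | 0.64 | 36% | 61% |
| Exponential | 0.48 | 52% | 49% |

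For the normal case: 2.802 × √0.636 = 2.235; 2.235 − 1.960 = 0.275; Φ(0.275) = 0.61. With the 48 evaluable patients assumed in Sample Size Determination, 48 × 0.64 gives the information of about 31 patients under normal dose, and 48 × 0.48 about 23 under exponential.

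**Doses squeezed by a limit.** For log-normal dose capped at 12 Gy, E at medians of 2, 3 and 5 Gy is 0.46, 0.53 and 0.68 (log-SD 0.75), and 0.47, 0.58 and 0.74 (log-SD 1.0). The loss is thus 26% to 54%. Uncapped log-normal dose with log-SD 1.0 gives E = 0.27.

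**Validity and simulation check.** Data were simulated at 0, 1, 3 and 6 months with random intercepts and slopes (slope SD 0.5, residual SD 1.0, both assumed), 4,000 runs per setting, with per-patient slopes regressed on dose.

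- Type I error of the split at n = 48 and n = 60: 0.047 to 0.052.
- Power at n = 48, continuous versus split: normal 0.79 v 0.59, uniform 0.80 v 0.65, exponential 0.75 v 0.46.

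**Functional form.** If the effect is linear in log dose and dose is log-normal, the split keeps 64%. Raw Gy keeps 75% at log-SD 0.75 but only 58% at log-SD 1.0. With the same doses capped at 12 Gy, raw Gy keeps 77% to 89% and the split 64% to 68%. If the truth is a step exactly at the median, the split loses nothing. Under exponential dose it is then about 2.1 times as efficient as a linear term, but only 0.52 and 0.19 times as efficient if the step is at the 75th or 90th percentile.

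**Common dose scale.** Biologically effective dose for total dose D in n fractions is D(1 + D/(n × 2.5)).

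- 12 Gy × 1: 12 × 5.8 = 69.6. Solving D(1 + D/7.5) = 69.6 gives 19.4 Gy in 3.
- 8.4 Gy × 1: 8.4 × 4.36 = 36.6, which gives 13.2 Gy in 3.
- 24 Gy in 3: 24 × 4.2 = 100.8. Solving D(1 + D/2.5) = 100.8 gives 14.7 Gy × 1.

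Nominal Gy from one- and three-fraction plans are therefore not comparable, even for ranking structures against a median. These conversions are for analysis only.

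**The case against.** **No error is alleged.** The test is valid, no figure is wrong, and the analysis is secondary and unpowered. That is true, and it limits the weight of the point.

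**The objective does not depend on it.** The time trends and the models linking imaging change to cognition do not use the split; only the added interaction does, and no estimate per Gy is promised. This also stands. But the interaction is the only planned test of whether dose relates to the trends.

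**Dose dependent need not mean graded.** The preliminary analyses under Radiation Planning Dose Constraints are themselves expressed as cut points. This weakens the inference about shape, but it gives no support for a cut at the sample median.

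**The sizes are assumed.** The loss runs from nothing to more than half, and 12 Gy is not a hard cap, because the standard plan is the default when sparing is not possible. The percentages show direction and plausible range, not the loss in this trial.

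**Flexible forms cost degrees of freedom.** Where a correct one-degree-of-freedom term has 80% power (noncentrality 7.85), a joint spline interaction test that captures all the signal has about 71% with two degrees of freedom and 64% with three. Two degrees of freedom therefore match the split for two-peaked doses and beat it in the other three cases. Three do worse than the split for two-peaked and uniform doses and gain little for normal. This is a fair point, and it favours a single pre-specified term for the main test.

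**Conversion error enters the covariate.** A high/low label is less sensitive to it, but the split needs the same conversion to rank mixed fractionations.

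**Conclusion.** The concern holds as a matter of efficiency and interpretability, not validity. Under a linear dose effect, the split loses roughly a fifth to a half of the dose information across the four basic shapes, and power falls from 80% to between 71% and 49%. These figures depend on assumed dose distributions and on the form of the effect. A step at the median would reverse the comparison, and a badly chosen continuous form can do slightly worse than the split. Whatever the shape, the planned analysis gives no estimate per unit of dose. The 3-month cognitive endpoint, on which the study is powered, is not touched. This is a change that should be made because it is cheap, not because the present test would mislead.

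**What to change.** In Secondary Objective Analyses:

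- Name one dose metric per structure, mean or maximum.
- Put one- and three-fraction doses on a common isoeffective scale with the protocol's own alpha/beta of 2.5 Gy, for analysis only.
- Make continuous dose by time the main test, with the form fixed in advance. A single term, for example log-transformed dose, is preferable. A low-degree-of-freedom spline can serve as a check on shape.
- Report the change in slope per unit of dose with its confidence interval.
- Keep the median split for plots or as a sensitivity analysis.

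The cost is small. No new data are needed, only the conversion for three-fraction patients and a little more analysis work. The team must also commit to a functional form on which the result will partly depend.
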